**VII.E. Project Description (E)**

**VII.E.1     *Will subjects be randomized?***

No

**VII.E.3     *Will any questionnaires, surveys, or written assessments be used to obtain data directly from subjects in this study?***

Yes

**VII.E.4     *List all questionnaires, surveys, written assessments and ATTACH each one to the application. (NOTE: You are NOT prohibited from attaching copyrighted materials to this application)***

There will be a pre-screening questionnaire and a screening questionnaire to collect information from the subjects. File name: Pre-Screening Questionnaire MCK, Screening Questionnaire MCK

A survey will be utilized to help determine an individuals eligibility to participate in the study. This survey can be found at <https://redcap.icts.uiowa.edu/redcap/surveys/?s=4XJ8CYKNCF>

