**DESCRIBE:**

- *What subjects will be asked to do/what happens in the study (in sequential order)*
- *The time period over which procedures will occur*
- *The time commitment for the subject for individual visits/procedures*
- *Long-term followup and how it occurs*

Following consent, a member of the study team will obtain the following demographic information directly from the subject: age, height, weight, and gender. A member of the study team will also identify the subject's Fitzpatrick skin type, and obtain a list of current medications and ongoing medical conditions. The subject will be asked to elaborate on the duration and severity of medical conditions and any treatments received. No medical records will be consulted to obtain or confirm this information. A member of the research team will use this information to screen out subjects meeting any of the exclusion criteria defined in VI.13. Subjects who pass the screening may proceed to the next step described below. Consent and screening procedures will take approximately 1 hour.

On Day 0 (may be the same day as consent is obtained), the subject will sit in a study room at the CRU for 30 minutes prior to any procedures. This allows the subject's skin to acclimate to the ambient environment in the study room (temperature, humidity). Following this acclimatization, the researcher will identify and mark with a marker 5 sites at each of the following 3 locations (for a total of 15 sites): upper arm, volar forearm, and abdomen. Hair may be clipped (but not shaved) at the sites if necessary. Noninvasive baseline measurements will be taken at each of the 15 sites as follows:

- Hydration will be measured by gently pushing a corneometer probe against the skin. The measurement will take less than 30 seconds at each site.
- Transepidermal water loss (TEWL) will be measured by resting a probe gently against the skin. This measurement will take 1-3 minutes at each site. (TEWL will only be measured on Day 0.)
- Electrical resistance (impedance) will be measured with an impedance meter by applying gel electrodes to each site and a reference electrode at a nearby site. The measurement will be repeated 3 times at each site, and will take less than 2 minutes total at each site.
- Skin color and redness will be measured by placing a colorimetry probe gently against each site. This measurement will take less than 30 seconds at each site.

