Following baseline measurements on Day 0, micropatches will be applied to three of each set of five sites. The sites will first be cleansed with an alcohol swab. A sterilized micropatch containing 50 tiny projections, each 800 um in length, will be placed perpendicular to the skin, and the researcher will apply gentle pressure to the back of the patch for 10 seconds. The researcher will then remove the patch, rotate it 45 degrees, and apply it again at the same site for another 10 seconds. This will create 100 micropores at each site. Micropatch application will only occur on Day 0.

Immediately after treating a site with a micropatch, TEWL and impedance measurements will be repeated. The site will then be covered with a sterile occlusive cover, and the researcher will apply a new micropatch array to the next site. Two sites at each location will not receive micropatch treatment. An occlusive covering will be placed over one of these two sites, and the other untreated site will remain uncovered. The 4 covered sites will be secured with medical tape. Note that all baseline measurements, micropatch applications, Day 0 post-micropatch measurements, and covering and medical tape placement will be performed at one anatomical location (5 sites) before proceeding to the next location. Day 0 procedures will require 3 - 4.5 hours.

Subjects will be asked to return to the CRU every 24 hours for 3 days. On each day hydration, impedance, and color measurements will be repeated at all sites. New occlusive material will be applied on Days 1 - 2. On Day 3 (the final day), covering will be removed, but not replaced. Procedures on Days 1-3 will last 2 - 3 hours.

Within 3-4 days after the Day 3 visit (or the last completed visit if a participant decides to drop out early) a study team member will contact the subject via phone or email to determine if the subject is experiencing any redness or irritation at the treatment site. No long-term follow-up will be necessary. The overall time commitment for this study is 9 - 13.5 hours in one week, across 4 study days if consent is obtained on Day 0, or 5 study days if consent is obtained before Day 0; consent may occur any time prior to study procedures.

**VII.E.7** *Will you attempt to recontact subjects who are lost to follow-up?*  
No - those lost to followup will not be recontacted

**VII.E.9** *Will subjects be provided any compensation for participating in this study?*  
Yes

**VII.E.10** *Cash*  
No

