## XI. Data Analysis

**XI.1** *Describe the analysis methods you will use, including, if applicable, the variables you will analyze*  
Descriptive statistics will be used for subject demographics. Each subject will serve as their own control, and paired t-tests will determine differences in TEWL (water loss measurements) and impedance from baseline to post-microneedle insertion. This will be used to determine if the microneedles adequately breached the skin barrier, demonstrated by a significant increase in TEWL from baseline and a significant decrease in impedance from baseline. For the colorimetry, and hydration measurements, each daily measurement will be compared to its baseline at that site, as well as to its hydration control (untreated, occluded site), using paired t-tests.  
Impedance data will be analyzed using similar methods as our previous study, and will ultimately be used to calculate the half-life of micropore closure. Z-pores values will be calculated from impedance measurements taken immediately following and over the days following microneedle treatment. These values will be converted to admittance (the inverse of impedance), which can demonstrate how “open” the micropores are in a very intuitive manner. If a micropore has a maximum admittance, then the micropore is 100% open. Using this information, we will plot admittance vs. time and calculate a rate constant of micropore admittance (k). The rate constant is then used to calculate the half-life of micropore closure, which thus describes a rate of closure in units of time. This micropore half-life will serve as the primary endpoint and will be compared among locations within a group, among groups within a location, and among locations in all groups.

**XI.2** *Provide the rationale or power analysis to support the number of subjects proposed to complete this study.*  

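### Day 0 takes the three locations one after another and the plan neither rotates nor records their order; if one order is used throughout, location cannot be separated from session position

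*Combined protocol and SAP*

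**What the plan says.** VII.E.6 has the researcher identify and mark "5 sites at each of the following 3 locations (for a total of 15 sites): upper arm, volar forearm, and abdomen". Before this, "the subject will sit in a study room at the CRU for 30 minutes prior to any procedures"; this happens once, ahead of the first location, and its stated purpose is to let the skin adjust to the room. Baseline readings, patch applications, post-patch readings and covering then follow in blocks, and the section gives the length of the visit in the next sentence: all of it "will be performed at one anatomical location (5 sites) before proceeding to the next location. Day 0 procedures will require 3 - 4.5 hours".

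XI.1 makes micropore half-life the primary endpoint, to be "compared among locations within a group, among groups within a location, and among locations in all groups". A difference in closure between body sites is one of the hypotheses in I.5.

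Nothing in VII.E.6 says which location comes first, whether the order is the same for every subject, whether it is repeated on Days 1-3, or whether it is written down. XI.1 has no term for order or session position. VII.E.1 asks "Will subjects be randomized" and is answered no; that concerns subjects, not locations.

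**The concern.** Every subject necessarily has a first, a second and a third location. The third is baselined, treated and re-measured well after the first, when the subject has been in the room much longer than the planned acclimatization. Patches are pressed on by hand, nine per subject, so technique could drift over the session. The interval from treatment to the Day 1 reading can also differ by location.

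If the same location is always first and the same one always last, these influences line up with location in every subject. Using each subject as their own control removes differences between subjects but not an order effect that all subjects share. A location difference in half-life, which is half of what the study sets out to find, could then be an order effect. If the order is not recorded, it cannot be adjusted for afterwards.

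**Working it through.** **Inputs from the documents.** Day 0 lasts 3-4.5 h, Days 1-3 last 2-3 h each, acclimatization takes 0.5 h, consent and screening about 1 h, and the overall commitment is 9-13.5 h (all VII.E.6). Completers: 10 in each of 5 groups, 50 in all (XI.2).

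**Assumptions.** Acclimatization lies inside the Day 0 time, the three locations take equal time, treatments and readings fall mid-block, visits start 24 h apart, and tests are two-sided at 5%. The plan states no alpha, SD or order effect.

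**1. The plan's own total.** 3 + 3×2 = 9 h and 4.5 + 3×3 = 13.5 h. Both match, and no separate hour is left for consent.

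**2. Time between first and third location.** Location work = Day 0 - 0.5 h = 2.5-4.0 h, or 0.83-1.33 h per location. The third location starts 2×0.83 = 1.7 h to 2×1.33 = 2.7 h after the first. If the consent hour is also inside Day 0, location work is 1.5-3.0 h and the lag is 1.0-2.0 h.

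**3. Separability.** Take a linear model with terms for subject (n columns), location (2) and position (2).
- One order for everyone: the position columns duplicate the location columns. Rank is 12 of 14 columns at n=10 and 52 of 54 at n=50, so the two effects cannot be separated at any sample size.
- Three orders in a Latin square: full rank (14 of 14, 54 of 54). Relative to 2σ²/n, the variance of a location contrast is multiplied by 1.0101 at n=10 and 1.0004 at n=50.

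**4. Illustration of the consequence.** Suppose there is no true location effect, one order is used throughout, and position shifts the mean paired difference by δ SD of that difference. The paired t statistic is noncentral t with n-1 degrees of freedom and noncentrality δ√n.

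| Assumed δ | n=10 | n=50 |
|---|---|---|
| 0 | 5% | 5% |
| 0.2 | 9% | 28% |
| 0.3 | 14% | 55% |

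**5. Clock time alone.** In a log-linear fit at nominal 0, 24, 48 and 72 h, the deviations from the mean time are -36, -12, 12 and 36, with sum of squares 2880. If all three follow-up readings are really d hours late relative to treatment, the fitted slope is multiplied by 1 + 36d/2880 = 1 + d/80, and half-life by 1/(1 + d/80).
- d = ±0.33 h: ∓0.4%.
- d = +2.67 h: -3.2%; d = -2.67 h: +3.5%.

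For scale, if the same order is kept on Day 1, the treatment-to-reading intervals for first and third location are 23.42 and 23.08 h (3 h and 2 h visits) or 23.33 and 22.67 h (4.5 h and 3 h visits), a gap of 0.3-0.7 h.

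**The case against.** The strongest reply is that the plan never states one order for everyone. The listing of upper arm, forearm and abdomen says which places to mark, not a working sequence. If the order varied haphazardly, much of the effect would be noise rather than bias. This stands, and it makes the point conditional. It is not a safeguard, because convenience can settle into one sequence and nothing would show afterwards whether it had.

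The block layout also gives some protection. Baseline, treatment and post-treatment readings at a location are close in time, each location has its own untreated occluded and open sites, and half-life comes from the admittance-time data at the treated sites. Additive drift shared by a location's readings is therefore partly removed. Drift in application, unequal acclimatization and elapsed time are not.

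XI.2 describes a pilot sized for feasibility. That limits what can be expected of it, but its data are meant to feed a later power analysis, and an order effect would carry through.

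Four stronger readings are tempting and are not supported:
- That location is confounded as the plan stands. This needs a common order, which no section states.
- That VII.E.1 rules out a varied location order. It is about randomizing subjects.
- That one operator tires over the session. VII.E.6 speaks only of the researcher and does not assign one person throughout.
- That intervals to Day 1 differ by 3.0-4.7 h between locations (24.75 v 21.75 h, or 25.33 v 20.67 h). This needs Day 1 run in the reverse of the Day 0 order, a different scenario from a constant order. Even the 4.67 h gap, if present on all three follow-up days, gives (1 + 1.33/80)/(1 - 3.33/80) = 1.06, about 6% in half-life between first and last location.

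Finally, XI.1 names no test for half-life across locations, so the paired t-test in the table is itself an assumption.

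**Conclusion.** The concern holds in conditional form. The plan does not prevent location from coinciding with session position in the among-location comparisons of the primary endpoint. If one order is used throughout, the overlap is complete and cannot be repaired in the analysis. Comparisons among race groups within a location are not affected by an order common to all groups.

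How large an order effect might be cannot be obtained from the documents. The error rates rest on assumed shifts of 0.2 and 0.3 SD and show sensitivity, not expectation; they matter more for the pooled comparison of about 50 subjects than within a group of 10. Timing error alone is a minor part of the problem. The change should be made because it is cheap and has to be in place before the first subject is treated.

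**What to change.** In VII.E.6, assign each subject one of three location orders (a Latin square of upper arm, forearm and abdomen) from a prepared list. Balance it within each race group, 4/3/3 in a group of ten, and vary which order takes the fourth subject so that 50 completers would split 17/17/16. Keep each subject's order on Days 1-3. Record the order used and the actual treatment and measurement times.

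In XI.1, use actual elapsed times in the admittance-time fit and include session position as a term in the location comparison.

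The cost is an allocation list, a few extra data fields and a variance increase for a location contrast of about 1% at n=10 and 0.04% at n=50. No extra subjects, staff or procedures are needed.

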This study aims to identify differences in micropore closure rates when microneedles are applied, through a micropatch, to different anatomical locations in volunteers of varied racial/ethnic groups. We hypothesize that there will be differences in micropore closure at the different body sites as well as among racial groups, as assessed by electrical impedance measurements. Micropore closure is indicative of skin barrier recovery.

**I.6** *Background and significance and/or Preliminary studies related to this project. (do not indicate "see protocol")*  
The skin is an ideal drug administration route (called transdermal delivery) because it overcomes many physiological limitations encountered with oral administration. Unfortunately, the number of topical products and patches currently available is limited because few drugs contain the necessary properties to pass through the hydrophobic, cohesive skin barrier. Many studies have demonstrated that pre-treatment with minimally invasive microneedles can bypass this barrier by creating micropores through which a drug can pass. Importantly, microneedles are well tolerated due to painless application and ease of use.

Microneedles create aqueous micropores in the epidermis that serve as channels for drug delivery. Micropore lifetime corresponds to drug delivery, and is therefore important in determining dosing and frequency of administration to achieve a desired therapeutic effect. Micropores are short-lived, healing within 2 hrs, but this lifespan can be extended to 48-72 hrs by occluding the site with a patch. Many structural and molecular skin characteristics, such as hydration, water loss, sebum content, skin cell size and maturity, and cohesion may affect micropore healing and other aspects in transepidermal drug delivery. These characteristics vary by anatomical site as well as race/ethnicity of the individual.

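### Does the unstated order of uncovering and re-covering sites on Days 1-3 distort the comparison of micropore half-lives?

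*Combined protocol and SAP*

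**What the plan says.** The Day 0 account in VII.E.6 is detailed. After a treated site is measured, "The site will then be covered with a sterile occlusive cover, and the researcher will apply a new micropatch array to the next site". It adds that "The 4 covered sites will be secured with medical tape" and that "covering and medical tape placement will be performed at one anatomical location (5 sites) before proceeding to the next location".

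The account of Days 1-3 is short: hydration, "impedance, and color measurements will be repeated at all sites. New occlusive material will be applied on Days 1 - 2". On visit length it says "Procedures on Days 1-3 will last 2 - 3 hours". It states no sequence, no cap on uncovered time and no recording of it. VII.B.11 says that no separate written protocol exists, so this is the operative text.

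Measurement times are in the Day 0 list. For impedance, "The measurement will be repeated 3 times at each site, and will take less than 2 minutes total at each site". Hydration and color each take under half a minute per site.

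I.6 gives the reason for the covers: "Micropores are short-lived, healing within 2 hrs, but this lifespan can be extended to 48-72 hrs by occluding the site with a patch". XI.1 fits one rate constant to admittance against time, converts it to a half-life (the primary endpoint), and compares it among locations and groups. It has no term for uncovered time.

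**The concern.** The covers define the condition under study, and every reading on Days 1-3 interrupts it. If an uncovered pore closes in about 2 h and a covered one in 48-72 h, a few uncovered minutes could do the work of hours of covered closure. The fitted half-life would then mix the two.

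Equal exposure everywhere does not remove the worry. Adding the same amount of fast closure to every site shortens a long half-life by more hours than a short one, so a real gap between locations would look smaller. The uncovered minutes also depend on handling: about 3 per site if each site is finished before the next, about 15 if a location's five sites are opened together, and 45 if all fifteen are.

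The size of the gap matters. XI.2 presents the study as a pilot to inform later power calculations, and I.6 says "Micropore lifetime corresponds to drug delivery, and is therefore important in determining dosing and frequency of administration".

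**Working it through.** **The plan's own time figures.** Day 0 takes 3-4.5 h and each of three later visits 2-3 h. 3 + 3×2 = 9 h and 4.5 + 3×3 = 13.5 h, which matches the stated overall commitment.

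**Inputs from the documents.** Readings at 0, 24, 48 and 72 h; at most 0.5 + 2 + 0.5 = 3 min of measuring per site on Days 1-3; 5 sites at each of 3 locations.

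**Assumptions.** Location A closes in 48 h and B in 72 h when covered (the ends of the I.6 range, which is not given by location). Closed means 10% of initial admittance; this choice sets the hours but not the share of the gap kept. Closed pores have no reading floor. A re-exposed pore closes in 2 h, with other values as sensitivity, because the documents do not give this rate.

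**Formula.** Covered rate k_c = ln(10)/lifetime: 0.04797 per h at A and 0.03198 at B. Uncovered rate k_u = ln(10)/2 = 1.1513. Let b and a be the uncovered minutes before and after each reading. A least-squares line through log admittance at the four times has slope k = k_c + (k_u − k_c)(b + 0.7a)/(60×24). Half-life = ln(2)/k.

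With no exposure: 0.6931/0.04797 = 14.45 h and 0.6931/0.03198 = 21.67 h, a gap of 7.22 h and a ratio of 1.50.

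**Same 2 h uncovered closure at both locations**

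| Handling (b/a, min) | A (h) | B (h) | Gap (h) | Lost |
|---|---|---|---|---|
| Site by site (3/0) | 13.79 | 20.20 | 6.41 | 11% |
| Location by location, read first (3/12) | 12.22 | 16.97 | 4.75 | 34% |
| Location by location, read last (15/0) | 11.66 | 15.88 | 4.23 | 41% |
| All sites open for the measuring, read last (45/0) | 8.41 | 10.35 | 1.94 | 73% |

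With 8 h uncovered closure, the 3/0 and 15/0 losses fall to 3% and 13%. If re-exposed pores close no faster than covered ones, nothing is lost.

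**Does the direction hold when the locations differ in uncovered closure too?** I.6 expects skin differences between sites to affect closure, so a common uncovered rate is a strong assumption. At 15 min, read last, A stays at 11.66 h:

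- Uncovered closure 2 h at A, 6 h at B: B = 19.45 h, gap 7.79 h (wider).
- 2 h at A, 8 h at B: B = 20.01 h, gap 8.35 h (wider).
- 2 h and 3 h, proportional to the covered lifetimes: B = 17.49 h, gap 5.83 h (19% lost), ratio still 1.50.

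So the shrinkage follows from the common-rate assumption. It is not a general property of equal exposure.

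**Is the contrast of 3 against 15 minutes secure?** Measuring takes 15×3 = 45 min, which leaves 75-135 min of a 2-3 h visit. Spread over 12 re-covers, that is about 6-11 min each. If a site stays open during its re-cover, site-by-site exposure is 3/6 to 3/11, and the gap is 5.49 to 4.86 h (24-33% lost with 2 h closure at both). Location-by-location exposure would rise as well, but the 11% figure for careful handling is then too favorable.

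**Can equal handling create a false difference?** If two locations share both k_c and k_u, the formula gives them the same k for any b and a. Every location has the same five sites and the same measurements, so the text builds in no unequal exposure.

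**The case for a change.** The strongest case for acting is that the text is silent on something that touches the primary endpoint, that uncovered minutes not logged cannot be recovered later, and that one sentence would settle it. Shorter exposure also keeps the fitted gap nearer the covered truth in the scenarios computed, including those where the gap widens: with 2 h and 8 h, 3 min gives 7.53 h against 8.35 h at 15 min. If staff opened all fifteen sites at once, the distortion under a common 2 h rate would be large.

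Most of that stands as a matter of good practice. The silence is real, and the text fits at least three handlings. A note of clock times would cost little and would allow a sensitivity analysis.

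It does not establish a fault in the plan. The extreme handling is not one that the text directs. The nearest written practice, on Day 0, covers each treated site before the next is treated and finishes one location before moving on; staff who carry it over are already doing what a clarification would ask. The 41% loss needs every treated site at a location to be read at the end of the block, which cannot be true of all three. Larger losses, or a reversal, arise only if a floor on closed-pore readings is added, which the documents do not describe. With an assumed 10% floor the gap is already only 1.0 h with no exposure at all. In a simulation with 10 completers, an assumed 30% CV and no floor, power is essentially unchanged (77%, 77% and 78% for no exposure, 3 min and 15 min).

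**Conclusion.** No change to the plan is needed. VII.E.6 leaves out a procedural detail for Days 1-3 that trained staff can fill sensibly from the Day 0 procedure. Each site has to be opened to be read, so some interruption of occlusion is unavoidable, and the text treats all locations and groups alike.

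Under a common 2 h uncovered closure time and no floor, about 11% of an assumed 7.22 h gap is lost at 3 min and 34-41% at 15 min. Under location-specific uncovered rates the same 15 min can widen the gap to 7.79-8.35 h, and under proportional rates the ratio of half-lives is untouched. Which of these applies depends on how fast a pore closes when re-exposed after a day or more under cover, and the documents do not say. No stated rule has been shown to give a wrong result, and equal handling does not produce a false difference between locations. In reporting, the half-life is best described as that of sites kept covered apart from brief daily measurement.
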